In order to further develop the skin assay Alcyomics is developing a human *in-vitro* 3D skin model using healthy volunteer skin cells (keratinocytes and fibroblasts) to form 3D skin model for testing in a 96 well format. The objective of our study is to use and evaluate a human *in vitro* skin explant assay for predicting DHRs to drugs, chemicals, cosmetics, biologics and peptides. The skin explant assay used in these studies was modified from the original predictive test, which has been extensively used to understand the underlying mechanism and immunobiology of graft versus host disease (GvHD) ([name] et al., 1999, [name] et al., 1988, Vogelsang et al., 1985), ([name] et al., 2002, Jarvis et al., 2002, Ruffin et al., 2011, Mavin et al., 2012, [name] et al., 2015). The modified assay (commercially known as Skimune®) has been used as a method for predicting skin sensitisation potential of chemical compounds ([name] et al., 2016). It has also recently been extended to test systemically administered LMW drugs that are associated (or not) with hypersensitivity reactions in the clinic. As previously described by [name] and colleagues, the assay is used in an autologous setting, when the different cell types and skin used in the assay are derived from the same donor. The assay involves isolation of peripheral blood mononuclear cells and separation of monocytes to derive dendritic cells which are activated with the compound (or peptide) of interest. The assay can then assess T cell proliferation, cytokine release, and histopathological damage to skin tissue due to any adverse immune reaction. The severity of the skin reaction is scored in severity from grade I-IV (Lerner et al., 1974) and a score of a grade II or above is used to predict a positive DHR.

In addition the assay can be used to predict any adverse immune reactions due to monoclonal antibody therapy – in this regard peripheral blood mononuclear cells are added directly onto autologous skin in the presence or absence of the test monoclonal.

We also aim to use the assay including the 3D skin assay for sensitivity testing other types of compounds e.g. cosmeceuticals which if the results is successful may reduce animal resting in the future and enable the design of safer drugs and compounds.

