## **3. STUDY DESIGN**

### **3.1 Healthy Volunteers**

- Assays will be conducted in the laboratory to assess the effect of the novel drugs or compounds on healthy volunteer blood or tissue.
- A minimal of 6 volunteers will be tested per compound at various dilutions in order to assess potency and effect of the compound on the blood or tissue.
- Lymphocyte proliferation ( known as T cell responses) will be measured as a surrogate to the potential proliferation of T cells and thus adverse effect of the drug on the healthy volunteer.
- The skin biopsy will be assessed for histopathological damage due to the effect of the T cells on the skin.
- Results from the assays (n=6 -10) will be analysed using non parametric statistical tests e.g. ANOVA and Mann –Whitney U tests using a PRISM statistical package

The analysis will be carried out by trained post-doctoral senior scientists and [name] at Alcyomics

All data will be coded with regard to the samples from the healthy volunteers.

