### **3.2 Sub-Study – Rheumatoid Arthritis (RA) Patients**

[figure not shown]
**Sub-study Group (1).** PBMC and skin biopsies obtained at a single time-point from 6-10 RA patients will be used to assess the safety of peptides as described for healthy volunteers (above in 3.1).

**Sub-study Group (2).** A cohort of 40-50 RA patients will be assessed for anti-drug antibody responses before and after antibody therapy over two years. This will involve a 70ml peripheral blood sample being taken pre-treatment (baseline) and 20ml blood sample being obtained post-treatment (12, 24, 36, 48, 60, 72, weeks). Skin biopsies will not be required from volunteers in this group.

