### 7.3 Skin Biopsy

Skin Biopsies will be performed in line with NuTH routine procedures. Two 4mm punch biopsies will be obtained from either the lower back, buttock or lower abdominal areas depending on volunteer or RA patient preference. The biopsy will be dissected into 10 pieces for the Healthy Volunteer and Group 1 RA study. Healthy volunteer biopsies may also be dissected and skin cells, fibroblasts and keratinocytes isolated and a 3D skin model developed in line with a high throughput assay development.

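### Section 3.1 labels ANOVA non-parametric and names the unpaired Mann-Whitney U test, although the assay's compound-versus-control and dilution contrasts are naturally within donor

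*Protocol*

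**What the plan says.** The analysis sentence for the explant assay is in Section 3.1: "Results from the assays (n=6 -10) will be analysed using non parametric statistical tests e.g. ANOVA and Mann –Whitney U tests". The same section says "A minimal of 6 volunteers will be tested per compound at various dilutions".

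Other sections describe the structure of the data:

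- Section 1 says "the assay is used in an autologous setting", meaning that "the different cell types and skin used in the assay are derived from the same donor". In the monoclonal version, blood cells are "added directly onto autologous skin in the presence or absence of the test monoclonal".
- Section 7.3 says "The biopsy will be dissected into 10 pieces for the Healthy Volunteer and Group 1 RA study".
- Section 1 also gives the rule for a positive result: "a score of a grade II or above is used to predict a positive DHR".

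The same approach carries over to other groups. Section 3.2 says that samples from 6-10 RA patients in Group 1 "will be used to assess the safety of peptides as described for healthy volunteers (above in 3.1". Section 3.3 has the surgical-skin experiments follow the healthy-volunteer design.

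The protocol gives no alpha, effect size, standard deviation, within-donor correlation or target power.

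**The concern.** Two things in the Section 3.1 sentence do not fit.

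First, ordinary ANOVA is not a non-parametric test. The reader cannot tell whether a parametric analysis is planned or a rank-based one such as Kruskal-Wallis or Friedman.

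Second, the one test named without ambiguity, Mann-Whitney U, assumes two independent groups. When treated and untreated material, or successive dilutions, come from the same donor, the results are linked. An unpaired test leaves donor-to-donor variation in the error term, although the design allows it to be removed.

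At stake are the outputs to which a test would be applied: T-cell proliferation (which Section 3.1 treats as a surrogate for adverse effect), cytokine release, and the dilution comparisons used to judge potency. With 6 to 10 donors there is little information to spare.

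**Working it through.** **No figure to reproduce.** The range n=6-10 is stated without a derivation.

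**Inputs.** From the protocol: 6 to 10 donors, autologous cells and skin, several dilutions per compound. Assumed, because not stated: two-sided 5%, normal response with total SD 1, a shift of 1 SD, within-donor correlation ρ from 0 to 0.9, and one treated and one control result per donor.

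**Mechanism.** With n donors, an unpaired test takes the variance of the mean difference as 2/n. The true variance is 2(1−ρ)/n. At ρ = 0.5 the true variance is half of what the test assumes, so the test rejects too rarely.

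**Normal-approximation check, n = 6, shift 1.** Power = Φ(shift/SE − 1.96).

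- Unpaired, calculated as if independent: SE = √(2/6) = 0.577; Φ(1.732 − 1.96) = 41%.
- Paired, ρ = 0.5: SE = √(1/6) = 0.408; Φ(2.449 − 1.96) = 69%.
- Paired, ρ = 0.7: SE = √(0.6/6) = 0.316; Φ(3.162 − 1.96) = 88.5%.

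These are optimistic at n = 6, so small-sample results follow.

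**Simulation, shift 1 SD, exact rank tests, 20,000 runs per cell.**

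| n | ρ | Mann-Whitney power | Signed-rank power | Paired t power | Mann-Whitney type I error |
|---|---|---|---|---|---|
| 6 | 0 | 30% | 19% | 29% | 4.2% |
| 6 | 0.3 | 28% | 27% | 39% | 2.1% |
| 6 | 0.5 | 27% | 36% | 51% | 1.1% |
| 6 | 0.7 | 26% | 54% | 71% | 0.4% |
| 6 | 0.9 | 26% | 93% | 99% | below 0.1% |
| 10 | 0 | 51% | 50% | 51% | 4.4% |
| 10 | 0.5 | 52% | 78% | 80% | 0.8% |
| 10 | 0.7 | 54% | 94% | 95% | 0.2% |

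A separate run at ρ = 0.8 and n = 6 gives about 26% for Mann-Whitney against 87% for the paired t-test, with Mann-Whitney type I error of 0.1-0.2%.

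**How the result moves with the shift.** At ρ = 0.5 and n = 10, Mann-Whitney against paired t is 11% against 30% for a shift of 0.5 SD, and 91% against 99% for 1.5 SD. At 2 SD both exceed 99%.

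**Limits of the signed-rank test.** With 6 donors its smallest two-sided p-value is 2/2⁶ = 2/64 = 0.031. A Bonferroni correction for only two contrasts needs 0.05/2 = 0.025, which it can never reach. On a four-level grade with many ties (assumed cut-points, n = 6, shift 2 SD, ρ = 0.5), Mann-Whitney had 82% power against 45% for signed-rank.

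**Unit of analysis.** Counting skin pieces as n works in the other direction. In a comparison between groups of donors, m pieces per donor multiply the variance of a group mean by 1 + (m − 1)ρ relative to what the test assumes. Two pieces at ρ = 0.5 give 1 + 0.5 = 1.5, so type I error is inflated. The same can happen within donors if they differ in their response to the compound.

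**The case against.** The strongest defence is that the sentence fixes very little. The tests are offered only as examples, no contrast is named, and the form of ANOVA is open. A repeated-measures or rank-based version would respect the donor structure, so independence is certain only for Mann-Whitney. Some comparisons are between donors: Section 1 has peptides tested in both healthy volunteers and RA patients, and an unpaired test suits a comparison of those groups. A statistical analysis plan that is not at hand may hold the detail. This is a laboratory study with no stated confirmatory hypothesis. All of this stands and limits the weight of the point. It does not rescue the label, and it leaves an unpaired test as the only clearly identified two-group method for a donor-blocked assay.

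A reader might infer more, in three ways that the documents do not support:

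- *That the named tests throw away most of the assay's power.* That depends on a correlation and shift the protocol does not give. At n = 10, ρ = 0.5 and a 1 SD shift, Mann-Whitney keeps 52/80, about 65%, of the paired t power. At ρ = 0 it loses nothing, and at n = 6 with low correlation it beats signed-rank.
- *That compounds will be wrongly passed as safe.* The positive call in Section 1 is a histology threshold at grade II, not a p-value, and nothing says that a non-significant test is read as safe.
- *That the error bars will be wrong.* The protocol describes none.

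**Conclusion.** The point holds in a limited form. The ANOVA label is wrong as written, and Mann-Whitney U does not match the within-donor contrasts that Sections 1, 3.1 and 7.3 imply. Used for those contrasts with 6 donors, a 1 SD shift and correlation of 0.5 to 0.8, it would run at a true type I error of about 1% or less and have about 26-27% power, against 51-87% for a paired t-test. The loss is small or absent at low correlation and shrinks with large shifts. All these sizes rest on assumed normal data, effect, correlation and alpha.

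The effect falls on proliferation, cytokine and dilution comparisons, and leaves the grade II rule untouched. It extends to RA Group 1 and surgical skin, which follow the healthy-volunteer design. This is a worthwhile correction of the analysis sentence, not a fault that undermines the study.

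**What to change.** Reword the Section 3.1 sentence:

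1. Remove the non-parametric label from ANOVA, or name the rank-based method that is meant.
2. For proliferation and cytokines, use a repeated-measures or mixed model with donor as random effect, comparing each dilution with the donor's own control.
3. For histology grade, use the Friedman test or a single within-donor trend test. Their power was not examined here. Avoid multiplicity-corrected signed-rank tests at 6 donors, given the 0.031 floor and their weakness on heavily tied grades.
4. Keep Mann-Whitney for comparisons between different donors, such as RA patients against healthy volunteers.
5. Define n as distinct donors, not skin pieces or repeat visits. Section 7.6 allows volunteers to be recalled for further samples, so this needs saying.
6. State that the wording also governs RA Group 1 and surgical skin.

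The cost is a wording change. No extra donors or samples are needed, and standard statistical software runs these analyses.

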### **3.2 Sub-Study – Rheumatoid Arthritis (RA) Patients**

[figure not shown]
**Sub-study Group (1).** PBMC and skin biopsies obtained at a single time-point from 6-10 RA patients will be used to assess the safety of peptides as described for healthy volunteers (above in 3.1).

**Sub-study Group (2).** A cohort of 40-50 RA patients will be assessed for anti-drug antibody responses before and after antibody therapy over two years. This will involve a 70ml peripheral blood sample being taken pre-treatment (baseline) and 20ml blood sample being obtained post-treatment (12, 24, 36, 48, 60, 72, weeks). Skin biopsies will not be required from volunteers in this group.

### **3.3 Sub-Study– Surgical Patients**

A single blood sample of 70ml will be obtained at a pre-clinic surgery visit. Excess skin samples taken at the time of surgery, which would normal be thrown away, (eg for breast reduction or amputation) will be used to carry out the experiments as per the healthy volunteer study design.

### 3.4 Flow Chart of the Study

## **4. STUDY SETTING**

Single centre study based in England with no other countries involved outside of the UK. Recruiting volunteers will be a joint role for the NHS team and Alcyomics. Sampling, obtaining consent and clinical procedure will be held at an NHS site, Newcastle upon Tyne. Scientific Review and statistical significance will be held at the private offices/laboratories of the study sponsor, Alcyomics Ltd.

## **5. RECRUITMENT**

### **5.1 Subject selection**

Two broad subject groups will be selected as follows:

#### **Healthy Volunteer Adults**

We wish to recruit healthy adult volunteers to donate two 4mm skin punch biopsies and a 70 ml blood sample. The skin and blood sample will be used for drug safety testing by the development of an assay that can be used to identify adverse reactions i.e. skin sensitisation and immunogenicity to various products including new drugs such as monoclonal antibodies, small molecule drugs and cellular therapies. This is a commercial assay. To date no such reliable assay exists to predict responses to new drugs in the laboratory and without the use of animal testing. The same samples will also be used for the development of an assay for atopic dermatitis

The number of subjects will be maximum of 300 per annum. The maximum sample size is determined by the estimated availability of participants and the resources in the laboratory to process samples

#### **Rheumatoid Arthritis (RA) Patients**

Our target populations of RA patients will be enrolled according to distinct but overlapping criteria to account for two pre-defined sub-study groups as follows:

Sub-study Group (1). RA patients known to have one of the following tissue types: HLADRB0401 or 0404 positive, irrespective of their background DMARD therapy.

Sub-study Group (2). RA patients being started on one of four classes of biologic DMARD (bDMARD; namely anti-TNF, anti-IL-6R or anti-CTLA4 or anti-CD20) that they have not previously received. Such patients will have experienced an inadequate response to conventional synthetic disease modifying anti-rheumatic drugs (csDMARDs), and may also have experienced an inadequate response to one or more treatment with a bDMARD (in one of the aforementioned classes) and/or targeted janus kinase inhibitor DMARD (tDMARD).

The number of RA subjects will be maximum of 40-50 per annum.

#### **Surgery Patients**

The surgery patients for example undergoing breast reduction or amputation surgery or patients where any surgery results in excess skin being thrown away, will be recruited at a pre-surgery clinic visit .

### **5.2 Enrolment criteria**

#### **Healthy Volunteers**

##### **Inclusion:**

- a. No underlying disease, such as cold or flu symptoms.
- b. No serious illness such as cancer requiring medication.
- c. Must speak and understand English

##### **Exclusion:**

- a. Skin pathology at the biopsy site (lower abdomen or buttock)
- b. Untreated/unresolved infective illness at the time of screening and/or baseline visit.
- c. Use of immunosuppressive medicines
- d. Evidence of allergy from questionnaire- see Appendix

### **Sub-Study – Rheumatoid Arthritis (RA) Patients**

#### **For RA Sub-study Group (1)**

(To assess the safety of peptides for potential use in clinical trial).

#### **Inclusion:**

- a. Clinical diagnosis of RA by a consultant rheumatologist with reference to accepted disease classification criteria.
- b. Known to be HLA-DRB1\*0401 or \*0404 positive
- c. Able and willing to provide written informed consent for study participation.
- d. Stable or no corticosteroid therapy within 4 weeks prior to screening visit.
- e. Must speak and understand English

#### **Exclusion:**

- a. Receipt of intramuscular/intra-articular corticosteroid and/or change in oral dose corticosteroid within 4 weeks of baseline visit.
- b. On >10mg daily dose prednisolone or equivalent corticosteroid therapy.
- c. Untreated/unresolved infective illness at the time of screening and/or baseline visit.
- d. Skin pathology at the biopsy site (lower abdomen or buttock)
- e. Evidence of allergy from questionnaire (*see Appendix*)

#### **For RA Sub-study Group (2)**

(To assess the responses of RA patients to biologics and monitor the response post therapy).

#### **Inclusion:**

- a. Clinical diagnosis of RA by a consultant rheumatologist with reference to accepted disease classification criteria.
- b. Treated with conventional and/or biologic and/or targeted therapy for RA in accordance with NICE guidelines.
- c. Clinical decision in accordance with current NICE guidelines to commence one of the following bDMARDs ((licensed biosimilar equivalents permitted): infliximab, adalimumab, etanercept, tocilizumab, abatacept or rituximab.
- d. Baseline blood sample must obtained prior to first dose of bDMARD to be prescribed in (c).
- e. Able and willing to provide written informed consent for study participation.
- f. Stable or no corticosteroid therapy within 4 weeks prior to screening visit..
- g. Enrolment of patients switching from one class of biologic therapy to another biologic (e.g. etanercept to adalimumab (both anti-TNF biologics) or an anti-IL6R) is permitted.
- h. Must speak and understand English

#### **Exclusion:**

- a. Receipt of intramuscular/intra-articular corticosteroid and/or change in oral dose corticosteroid within 4 weeks of baseline visit.
- b. On >10mg daily dose prednisolone or equivalent corticosteroid therapy.
- c. Contraindication to biologic therapy under NICE guidance and/or local practice.
- d. Untreated/unresolved infective illness at the time of screening and/or baseline visit

### **Surgery Patients**

#### **Inclusion:**

- a. No acute underlying disease, such as cold or flu symptoms.
- b. No serious illness such as cancer requiring medication.
- c. Must speak and understand English

#### **Exclusion:**

- a. Skin pathology at the biopsy site (lower abdomen or buttock)

- b. Untreated/unresolved infective illness at the time of screening and/or baseline visit.
- c. Use of immunosuppressive medicines
- d. Evidence of allergy from questionnaire- see Appendix

### 5.3 Study Timeline

#### Healthy Volunteers

Months 1-59:

- Recruitment of patients
- Data Collection

Month 60: Completion of Study

#### RA Patients

Months 1-18:

- Recruitment of patients
- Data Collection
- Disease activity calculations

Months 18-24:

- Data Analysis Correlation with clinical outcomes

Month 24: Completion of study

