## STUDY SUMMARY

Study Title	Development of an in vitro assay for drug safety and efficacy and skin sensitivity
Internal ref. no. (or short title)	Safety testing of novel compounds and drugs
Study Design	Laboratory
Study Participants	Healthy Volunteers / Rheumatoid Arthritis (RA) Patients /Surgical Patients ( Sub-Studies )
Planned Size of Sample (if applicable)	
Healthy Volunteer          Recruit 4-6 participants per week          1 set of skin punch biopsy (2 biopsies per set) per healthy volunteer          60-70ml blood per healthy volunteer          For patients who have opted in to consent to provide further samples a maximum of 3 sets of skin punch biopsies (2 biopsies per set) and 3 sets of 70 ml of blood.
 
Sub-Study : Rheumatoid Arthritis Patients          Recruit 40-50 per 12 months, 80-100 over 24 months          1 x 60-70ml blood and further maximum 120ml in serial (20ml x 6 blood samples)
 
Sub-study :Surgical Patients          1x 70ml blood at pre-surgical clinic visit          Excess skin sample taken at time of surgery ( minimum 2x 4mm)

Follow up duration (if applicable)	NA
Planned Study Period	5 years
Research Question/Aim(s)	The development and use of in vitro skin assays to predict adverse responses to compounds including drugs and cellular therapies
Funder and financial and non-financial support given	
Alcyomics Ltd - Payment of research staff, research nurses, funding study consumables, vouchers for participants.
 
Vouchers  Healthy Volunteer:
 
 
£50.00 voucher for 1 set of skin biopsies (2 biopsies per set) and 1 set of 70ml blood sample
 
 
For patients who have opted in to consent to provide further samples:
 
 
£25.00 voucher per 70 ml blood sample and £25.00 voucher per 1 set of skin punch biopsy (2 biopsies per set)
 

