### 7.4 Follow-up Samples

#### 7.4.1 Healthy Volunteer / RA Patient Sub-Study Group 1

- Samples ( taking of 2x 4mm biopsies or extra 70ml blood sample) will be taken either at the same time as the baseline visit or + 7 to 14 days after baseline as directed according to laboratory requirements and patient availability:

2 x 4mm Skin biopsy (defined as 1 x skin biopsy). The skin biopsies are dissected and used for the skin assay.

Patients enrolled in this group will only require further follow up for the removal of sutures, as indicated in the study flow chart, one week after the biopsy (see *Schedule of Events*, 7.5.1, Table 1).

#### 7.4.2 RA Sub-study Group 2

These patients will be followed prospectively in order (i) to determine treatment response and (ii) to monitor for the development of anti-drug antibodies by the developed *in vitro* test and confirmatory serum anti-drug antibody assays and drug levels. Follow-up visits will take place at weeks 12(+/- 2 weeks), 24

(+/- 2 weeks), 36 (+/- 2 weeks), 48 (+/- 2 weeks), 60 (+/- 2 weeks), and 72 (+/- 2 weeks),. At each of these visits the following procedures will be undertaken (see also *Section 7.5, Table 2*):

- Patient Global Health questionnaire (visual analogue scale).
- Physician-reported Global Assessment questionnaire (visual analogue scale).
- 28-joint swollen and tender joint count (SJC, TJC).
- Blood test for CRP and ESR (NHS laboratories).
- Blood draw for research (20ml). 15ml blood is used to develop the anti-drug antibody assay and 5ml as serum to screen for anti-drug antibodies.
- The DAS28-CRP, DAS28-ESR and CDAI scores will be calculated (awaiting results of contemporaneous blood results where needed)

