## 8.3 End of Study

The study will terminate when the required number of patients have been enrolled and have completed follow-up.

However, the study will end prematurely if

- The Ethics Committee mandate so
- The sponsor mandates so

The approving REC will be notified in writing if the study has been concluded or terminated early.

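### The RA timeline in section 5.3 cannot be kept together with the 72-week Group 2 visit schedule: with recruitment to month 18, the last visit falls about 11 months after the stated completion

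*Protocol*

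**What the plan says.** Section 5.3 of the protocol (Study Timeline, RA Patients) lists under months 1-18 "Recruitment of patients", together with data collection and disease activity calculations. Months 18-24 are given to "Data Analysis Correlation with clinical outcomes". The last entry is "Month 24: Completion of study".

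The Group 2 schedule is longer. Section 3.2 says "A cohort of 40-50 RA patients will be assessed for anti-drug antibody responses before and after antibody therapy over two years", with a baseline sample and then a "20ml blood sample being obtained post-treatment (12, 24, 36, 48, 60, 72, weeks". Section 7.4.2 repeats the visits with their windows ("36 (+/- 2 weeks), 48 (+/- 2 weeks), 60 (+/- 2 weeks), and 72 (+/- 2 weeks"), and Table 2 in section 7.5 schedules research blood, joint counts, global assessments and disease activity scores at every one of them.

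Three other statements bear on the timeline:
- Section 8.3: "The study will terminate when the required number of patients have been enrolled and have completed follow-up".
- Study Summary: RA recruitment of 40-50 per 12 months and 80-100 over 24 months, a follow-up duration of NA, and a planned study period of 5 years.
- Section 5.1: at most 40-50 RA subjects per annum.

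**The concern.** The sections give staff two instructions that cannot both be carried out. Section 5.3 closes the RA work at month 24 and lists no data collection after month 18. Table 2 requires visits that, for anyone enrolled later than about month 7, fall after month 24.

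Group 2 exists to determine treatment response and to monitor for anti-drug antibodies prospectively (section 7.4.2). If the calendar in 5.3 were enforced, the later visits would be observed only in patients who enrolled early, and that subset would be spread over up to four classes of biologic (section 5.1). If the visit schedule were kept, the dates for analysis and completion would be wrong. The protocol does not say which gives way.

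**Working it through.** **Inputs**
- Recruitment and data collection in months 1-18, analysis in months 18-24, completion at month 24 (section 5.3).
- Last Group 2 visit at week 72, window +/- 2 weeks (sections 3.2 and 7.4.2, Table 2).
- Group 2 cohort of 40-50 (section 3.2); RA accrual of 40-50 per 12 months (Study Summary).
- Assumptions: a month of 30.44 days, and enrolment counted from the baseline visit.

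**Can month 24 be reproduced?**
- 72 weeks = 72 x 7 / 30.44 = 16.56 months; 74 weeks = 74 x 7 / 30.44 = 17.02 months.
- Last visit of a patient enrolled at month 18: 18 + 16.56 = 34.6, or 18 + 17.02 = 35.0 at the end of the window. Month 24 is not reproduced; the gap is 34.6 - 24 = 10.6 to 35.0 - 24 = 11.0 months.
- At month 24 that patient has been followed for 6 x 30.44 / 7 = 26 weeks.
- Latest baseline that allows week 72 by month 24: 24 - 16.56 = month 7.4. By month 18: 18 - 16.56 = month 1.4.
- If the whole cohort enrolled within 12 months, the last visit would still fall at 12 + 16.56 = month 28.6.

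**Share able to reach each visit, assuming uniform accrual over months 0-18**

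Share = (C - visit in months) / 18, capped at 100%, where C is the month at which visits stop.

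| Visit (week) | C = 24 | C = 18 |
|---|---|---|
| 12 | 100% | 85% |
| 24 | 100% | 69% |
| 36 | 87% | 54% |
| 48 | 72% | 39% |
| 60 | 57% | 23% |
| 72 | 41% | 8% |

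For week 72, (24 - 16.56)/18 = 41%, which is about 17-21 of 40-50 patients; (18 - 16.56)/18 = 8%, about 3-4 patients.

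**Sensitivity of the week-72 share to accrual, closure at month 24**
- Cohort enrolled uniformly over 12 months, at the Summary's rate: 7.44/12 = 62%.
- Uniform over 24 months: 7.44/24 = 31%.
- Linearly rising over 18 months: (7.44/18)^2 = 17%.
- Linearly falling over 18 months: 1 - (1 - 7.44/18)^2 = 66%.
- Uniform over 18 months, at the window limits: 44% at week 70 and 39% at week 74.

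None reaches 100%. That would need all enrolment to finish by about month 7.4.

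**The case against.** Section 5.3 is a planning timeline and does not order visits to stop. Section 8.3 ties the end of the study to completed follow-up, and the overall study runs to month 60. A team that followed 8.3 would lose no visits; the RA read-out would simply slip. This stands, and it means that lost data is one possible outcome and not a certain one. It does not remove the conflict: month 24 is labelled as completion, and section 3.2 also speaks of two years, so month 24 does not look like a slip.

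The size is also open to challenge. Section 5.3 lists recruitment and data collection under one heading and does not say that enrolment continues to month 18. At the Study Summary's own rate a cohort of 40-50 would enrol in about 12 months, and 62% could then reach week 72 by month 24. This stands too. A reader might infer that most of the cohort must lose its final visit. The documents do not support that, because the figure depends on an accrual pattern they do not give.

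A reader might also infer that the aim of Group 2 is defeated. Even with closure at month 24 and recruitment to month 18, weeks 12 and 24 are fully covered. Response after therapy is a secondary objective (section 2.2), and week 72 is nowhere named as the key time point.

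Finally, the NA for follow-up duration is minor, since the Summary covers several populations and Group 2 follow-up is specified elsewhere.

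**Conclusion.** The inconsistency is real and is confined to RA Sub-study Group 2. Group 1 is sampled at a single time-point and fits the timeline. With recruitment to month 18, the last Group 2 visit falls at about month 34.6-35, some 11 months after the stated completion. This rests only on the protocol's dates and the length of a month. Section 8.3 is a second, conflicting end rule, and nothing in the protocol reconciles the two.

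How many patients would miss week 72 if month 24 were enforced rests on assumed accrual. The share able to reach it is about 41% with uniform accrual over 18 months, about 62% if the cohort enrols within 12 months, and about 17-66% across the patterns tried. It is about 8% if data collection stops at month 18 as listed, with uniform 18-month accrual. None of these should be quoted without its assumption.

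**What to change.** Amend section 5.3 so that Group 2 data collection runs to the last patient's week-72 visit, about month 35 if recruitment runs to month 18. Keep the six-month analysis after it, with completion at about 35 + 6 = month 41. This is inside the 5-year period if the RA clock starts with the study. The amendment should say when month 1 is, because the protocol does not anchor it.

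In the same amendment:
- Reconcile the two-year statement in section 3.2 with the visit schedule.
- Reconcile the Summary's 80-100 over 24 months with the 18 months in section 5.3 and the cohort of 40-50. Recruitment over 24 months would move the last visit to 24 + 16.56 = about month 40.6.
- Replace NA with 72 weeks for Group 2 in the Summary.
- Make section 8.3 and the RA completion date agree.

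Keeping month 24 and closing recruitment at about month 7 is not a good alternative. The last visit would fall at month 24, leaving no time for analysis. At 40-50 per 12 months, 7.44 months would yield only 7.44 x 40/12 = 25 to 7.44 x 50/12 = 31 patients, short of the 40-50 planned.

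The cost is an RA read-out about 41 - 24 = 17 months later than stated. No patients, visits or procedures are added.
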